7.5 Study stopping rules for immune-related toxicity

There is the potential for increased immune-related adverse events with combination of umbralisib and pembrolizumab. The study will be suspended and an ad hoc safety committee will be convened with individuals with appropriate expertise (majority of whom are not directly affiliated with the study) for consideration of results and appropriate modification or termination of the study if there is

sufficient evidence that the probability of Grade 3 or 4 immune-related adverse events that do not resolve to Grade ≤ 2 within 72 hours exceeds 20%. This will be deemed to occur if the lower level of a one-sided 80% confidence interval for this proportion exceeds 20%.

The protocol was originally written to determine if there was sufficient evidence that the probability of grade 3-4 immune-related adverse events exceeded 10%. This was based on earlier data, though follow up data from a study that combined umbralisib with pembrolizumab and a CD20 monoclonal antibody found 4/20 (20%) subjects had grade 3-4 transaminitis. This protocol hit the suspension rule when 2 out of the first 5 subjects met this (grade 3 rash and grade 3 ALT elevation).

An ad hoc safety committee was convened. Since there are no standard therapies beyond PD1 inhibitors in the treatment of classical Hodgkin lymphoma, it was felt that a higher threshold for toxicity was warranted. Therefore, the threshold was increased to suspend again if the lower level of a one-sided 80% confidence interval for this proportion exceeds 20% (increased from 10%)

In addition, a change was recommended to allow for prednisone treatment that exceeds 10 mg for 6 weeks before requiring discontinuation of the protocol.

There are 15 subjects remaining in the study to be enrolled. The study operation rules will include the first two subjects as meeting this criteria, and will mandate another suspension in the following circumstances

- If 4 out of the first 11 or fewer patients, or 5 out of the first 15 or fewer, or 6 out of 20 or fewer patients experience Grade 3 or 4 immune-related adverse events that do not resolve to Grade ≤ 2 within 72 hours.

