8.0 DOSAGE MODIFICATION, DELAY, OR DISCONTINUATION

8.1 Dose modification of pembrolizumab

8.1.1 Withholding pembrolizumab: Adverse events (both non-serious and serious) associated with pembrolizumab exposure may represent an immunologic etiology. These adverse events may occur shortly after the first dose or several months after the last dose of treatment (see below). The use of corticosteroids should be considered for management of immune-related adverse events (irAEs). Please refer to prescriber

manual for further detail on dosing of corticosteroids for pembrolizumab-related toxicity. If the drug-related toxicity does not resolve to Grade 0-1 within 4 weeks after onset of toxicity, discontinuation is recommended. Pembrolizumab must be withheld for drug-related toxicities and severe or life-threatening AEs as per the below criteria (may resume upon recovery to grade 0 or 1 toxicity unless otherwise noted below).

- Hematological toxicity- Grade 4; Pembrolizumab should be held until resolved to Grade ≤ 3 .
- Colitis, any Grade- Grade 2-3; also administer high-dose systemic corticosteroids (followed by a taper).
- Hyperthyroidism- Grade 3; administer high-dose systemic corticosteroids (followed by a taper).
- Hypophysitis- Grade 2-4; administer high-dose systemic corticosteroids (followed by a taper).
- Nephritis- Grade 2; consider administration high-dose systemic corticosteroids (followed by a taper).
- Pneumonitis- Grade 1-2; administer high-dose systemic corticosteroids (followed by a taper). Pembrolizumab may be resumed after resolution.
- Hepatitis- Grade 2-3. Pembrolizumab should be held until resolution to Grade ≤ 1 . If the subject has baseline liver involvement and Grade 2 abnormalities at baseline, treatment may continue unless it worsens to Grade 3.
- Other treatment-related toxicity, severe or Grade 3; may require high-dose systemic corticosteroids (based on severity). Upon improvement to grade 0 or 1, initiate corticosteroid taper and continue to taper over at least 1 month. Restart pembrolizumab if the adverse reaction remains at grade 0 or 1 and steroid dose is ≤ 10 mg. Please refer to the FDA approved pembrolizumab prescribing information for more information.

8.1.2 Discontinuing Pembrolizumab: If any of the following criteria are met, pembrolizumab should be permanently discontinued

- Confirmed radiographic disease progression per the appropriate tumor evaluation criteria.

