11.0 STATISTICAL CONSIDERATIONS

11.1 The primary objective of this study is to estimate the CR rate of this regimen. In a population of CHL patients who have failed after autologous transplant, the CR rate of single agent pembrolizumab is 16%². Targeted accrual is 20 subjects. If the assumed-true CR is 40%, we will have 88% power to observe a statistically significantly higher CR than the fixed rate of 16% with 20 subjects (at the one-sided significance level of 0.1). The 95% confidence interval (CI) by exact Clopper Pearson for the proposed 40% CR is from 19% to 64%, which will reasonable exclude a response rate of < 16%. With 20 subjects, CI will change to 27% to 73% with estimated CR 50%, and 36% to 81% with estimated CR 60%

11.2 Anticipated accrual: We anticipate accrual of 20 subjects over 2 years.

11.3 Descriptive summary statistics for continuous variables will include sample size, mean, standard deviation (SD), median, minimum and maximum for both baseline and post-baseline measurements (if applicable). Summary statistics for categorical variables will include sample size, frequency and percentages.

11.4 Estimated distribution of study population by gender and race and ethnicity:

Ethnic Category	Females	Males	Total
American Indian/Alaska Native			
Asian	1	1	2
Native Hawaiian or Other Pacific Islander	0	0	0
Black or African American	0	1	1
White	7	10	17
More than one race	0	0	0
Unknown or not reported	0	0	0
Racial Categories: Total of all subjects	8	12	20

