12.5 Data Safety and Monitoring Plan-

Institutional support of trial monitoring will be in accordance with the FHCRC/University of Washington Cancer Consortium Institutional Data and Safety Monitoring Plan. Under the provisions of this plan, FHCRC Clinical Research Support coordinates data and compliance monitoring conducted by consultants, contract research organizations, or FHCRC employees unaffiliated with the conduct of the study. Independent monitoring visits occur at specified intervals determined by the assessed risk level of the study and the findings of previous visits per the institutional DSMP.

In addition, protocols are reviewed at least annually and as needed by the Consortium Data and Safety Monitoring Committee (DSMC), Fred Hutchinson Cancer Research Center (FHCRC) Scientific Review Committee (SRC) and the FHCRC Institutional Review Board (IRB). The review committees evaluate accrual, adverse events, stopping rules, and adherence to the applicable data and safety monitoring plan for studies actively enrolling or treating subjects. The IRB reviews the study progress and safety information to assess continued acceptability of the risk-benefit ratio for human subjects. Approval of committees as applicable is necessary to continue the study.

The trial will comply with the standard guidelines set forth by these regulatory committees and other institutional, state and federal guidelines.

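### Section 7.5 conflicts with itself at three immune-related events in seven or fewer subjects: the confidence-bound rule calls for suspension, but the operational list has no three-event entry.

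*Combined protocol and SAP*

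**What the plan says.** The event of interest is a Grade 3 or 4 immune-related adverse event that has not improved to Grade 2 or lower within 72 hours. Section 7.5 of the combined protocol and SAP gives two statements of when such events suspend the trial.

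The first is general. When there is enough evidence that the event probability is above 20%, "The study will be suspended and an ad hoc safety committee will be convened". The evidence standard is a confidence bound, in percent: "This will be deemed to occur if the lower level of a one-sided 80% confidence interval for this proportion exceeds 20". The section repeats this as the revised threshold, raised from 10%. No minimum event count or number of subjects is attached, and no interval method is named.

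The second is an operational list, written after the trial had already been suspended once: "This protocol hit the suspension rule when 2 out of the first 5 subjects met this". With 15 subjects still to enrol, the section says: "The study operation rules will include the first two subjects as meeting this criteria, and will mandate another suspension in the following circumstances". The circumstances are "If 4 out of the first 11 or fewer patients, or 5 out of the first 15 or fewer", and finally 6 in 20 or fewer. Nothing says whether the list illustrates the general rule or replaces it.

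**The concern.** The list starts at four events, yet the trial restarts with two events in five subjects. The next possible count is three, and a third event in the next one or two subjects gives 3/6 or 3/7, which are small denominators with a high observed rate. If the confidence bound exceeds 20% there, one sentence of section 7.5 suspends the study and the list does not.

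This is the only study-level numerical safety rule in the protocol, and its earlier form has already fired once. Staff who work from the list alone would keep enrolling after the stated criterion had been met. The oversight bodies in section 12.5 would not settle the matter by themselves, because their remit includes the rule: "The review committees evaluate accrual, adverse events, stopping rules, and adherence to the applicable data and safety monitoring plan". They would find two versions of it.

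**Working it through.** **Inputs.** From section 7.5: one-sided 80% bound; threshold 20%; 2 events in 5 subjects carried forward; 15 subjects to come; list limits of 4 in 11, 5 in 15 and 6 in 20. From section 11.1: target of 20 subjects. Section 11.1 names an interval method, but only for the complete response rate: "The 95% confidence interval (CI) by exact Clopper Pearson for the proposed 40% CR". Using the exact method for section 7.5 is therefore an assumption, tested in step 1.

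**Step 1: reproduce the list.** The exact one-sided 80% lower bound for x events in n subjects is the 0.20 quantile of a Beta(x, n − x + 1) distribution. It exceeds 20% exactly when P(X ≥ x | n, 0.20) is below 0.20.

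| Events/subjects | Lower bound | Above 20%? | On the list? |
|---|---|---|---|
| 4/11 | 21.7% | yes | yes |
| 4/12 | 19.8% | no | no |
| 5/15 | 21.3% | yes | yes |
| 5/16 | 19.9% | no | no |
| 6/20 | 20.1% | yes | yes |

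All three limits are reproduced. Wald bounds would give limits of 12, 17 and 21, and Wilson bounds 13, 17 and 22. Continuity-corrected Wald, continuity-corrected Wilson, Agresti-Coull, Jeffreys and mid-p bounds also fail to give all three.

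**Step 2: apply the same formula to two and three events.**

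| Events/subjects | Lower bound | P(X ≥ x) at 20% | Above 20%? | On the list? |
|---|---|---|---|---|
| 2/5 (restart) | 16.9% | 0.263 | no | no |
| 3/6 | 26.9% | 0.099 | yes | no |
| 3/7 | 22.8% | 0.148 | yes | no |
| 3/8 | 19.9% | 0.203 | no | no |

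The boundary implied by the stated rule is 3 in 7, 4 in 11, 5 in 15 and 6 in 20. The list holds the last three. The restart also fits this method: 16.9% is above the old 10% threshold and below the new 20%.

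**Step 3: does the interval method matter?** At 3/7 the Wald bound is 27.1% and the Wilson bound 28.5%. Every 80% variant tried puts 3/6 above 20%. Only continuity-corrected Wald puts 3/7 below, at 19.97%, and that method gives list limits of 10, 14 and 18, not those in the plan.

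**Step 4: consequences from 2/5.** Let p be the true event rate. The chance of a third event in subject 6 or 7 is 1 − (1 − p)². At p = 30% this is 1 − 0.7² = 0.51. The other figures come from a forward recursion over subjects 6 to 20, comparing the list with the list plus 3 in 7.

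| True rate | Third event in subject 6 or 7 | Ever suspended: list / rule | Mean enrolment at suspension or at 20: list / rule |
|---|---|---|---|
| 10% | 19% | 15% / 26% | not tabulated |
| 20% | 36% | 49% / 58% | 15.8 / 13.6 |
| 30% | 51% | 79% / 83% | 12.9 / 10.8 |
| 40% | 64% | 94% / 95% | 10.7 / 8.9 |

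Given a third event in subject 6 or 7, using the list alone enrols a further 6.0, 4.0 and 2.8 subjects on average before suspension or reaching 20, at true rates of 20%, 30% and 40%. It never suspends in 25%, 8% and 2% of those cases. As a check at 30%: 0.51 × 3.99 = 2.03, which equals the unrounded difference in mean enrolment, 12.87 − 10.83 = 2.04, to rounding.

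**The case against.** The strongest reply is that there is no true contradiction. The list does not claim to be exhaustive, so the general sentence still suspends the study at 3/6 and 3/7, and the list is merely an incomplete set of worked cases. Alternatively, the list is later and more specific, was written after a committee had reviewed 2/5, and may have been meant to govern so that a single further event would not stop the trial again. Each reading removes the conflict, but they require opposite actions at 3/6 and 3/7, and the text chooses neither.

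A second reply is that the effect is small. This is partly right. The chance of ever suspending differs by 4 points at a true rate of 30% and 1 point at 40%, while the three-event line adds 11 points at 10% and 9 points at 20%. Under the exact method the list and the rule agree from subject 8 onward. Annual and as-needed committee review (section 12.5) and the subject-level hold rules (section 8) operate regardless. These facts bear on how to reconcile the text, not on whether two versions can stand.

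Two details also stand. A fourth event first occurring after subject 11 triggers nothing under either version, since 4/12 gives 19.8%. And a late event in one of the first five subjects would give 3/5 (32.7%), a further state that meets the rule without appearing on the list.

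**Conclusion.** The concern holds and needs correcting. At exactly three events in seven or fewer subjects, the confidence-bound rule requires suspension and the operational list does not. These are the first states at which the rule can be met again after the restart, and they are likely to arise if the true rate is 20% or more. The practical loss from using the list alone is later suspension, by about two subjects on average across all paths, rather than a large change in whether the study is ever suspended.

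The conflict itself needs only the stated rule and a standard interval method. The operating figures also assume independent events, counted in enrolment order and known before the next subject enrols. Section 8.1.1 warns against the last assumption: "These adverse events may occur shortly after the first dose or several months after the last dose of treatment". The real figures could therefore differ in either direction. The documents do not show whether the ad hoc committee left three events out on purpose.

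**What to change.** Reconcile the two statements in section 7.5, in one of two ways:

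- If the confidence bound governs, complete the list from it. By the exact method the added entry is 3 in 7 or fewer.
- If the committee meant to leave three events out, state that the list overrides the confidence bound.

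In either case, name the interval method. It matters at the restart itself: at 2/5 a Wald bound (21.6%) or a Wilson bound (23.9%) already exceeds 20%, whereas the exact bound (16.9%) does not.

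The wording cost is one line. Adding the entry also has an operating cost: given 2/5, the chance of another pause for committee review rises from 15% to 26% at a true rate of 10%, and from 49% to 58% at 20%. The committee should weigh these extra pauses against earlier suspension when the rate is excessive. This review does not say which choice is right.

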8.0 DOSAGE MODIFICATION, DELAY, OR DISCONTINUATION

8.1 Dose modification of pembrolizumab

8.1.1 Withholding pembrolizumab: Adverse events (both non-serious and serious) associated with pembrolizumab exposure may represent an immunologic etiology. These adverse events may occur shortly after the first dose or several months after the last dose of treatment (see below). The use of corticosteroids should be considered for management of immune-related adverse events (irAEs). Please refer to prescriber

manual for further detail on dosing of corticosteroids for pembrolizumab-related toxicity. If the drug-related toxicity does not resolve to Grade 0-1 within 4 weeks after onset of toxicity, discontinuation is recommended. Pembrolizumab must be withheld for drug-related toxicities and severe or life-threatening AEs as per the below criteria (may resume upon recovery to grade 0 or 1 toxicity unless otherwise noted below).

- Hematological toxicity- Grade 4; Pembrolizumab should be held until resolved to Grade ≤ 3 .
- Colitis, any Grade- Grade 2-3; also administer high-dose systemic corticosteroids (followed by a taper).
- Hyperthyroidism- Grade 3; administer high-dose systemic corticosteroids (followed by a taper).
- Hypophysitis- Grade 2-4; administer high-dose systemic corticosteroids (followed by a taper).
- Nephritis- Grade 2; consider administration high-dose systemic corticosteroids (followed by a taper).
- Pneumonitis- Grade 1-2; administer high-dose systemic corticosteroids (followed by a taper). Pembrolizumab may be resumed after resolution.
- Hepatitis- Grade 2-3. Pembrolizumab should be held until resolution to Grade ≤ 1 . If the subject has baseline liver involvement and Grade 2 abnormalities at baseline, treatment may continue unless it worsens to Grade 3.
- Other treatment-related toxicity, severe or Grade 3; may require high-dose systemic corticosteroids (based on severity). Upon improvement to grade 0 or 1, initiate corticosteroid taper and continue to taper over at least 1 month. Restart pembrolizumab if the adverse reaction remains at grade 0 or 1 and steroid dose is ≤ 10 mg. Please refer to the FDA approved pembrolizumab prescribing information for more information.

8.1.2 Discontinuing Pembrolizumab: If any of the following criteria are met, pembrolizumab should be permanently discontinued

- Confirmed radiographic disease progression per the appropriate tumor evaluation criteria.
- Immune-mediated Pneumonitis – discontinue for Grade 3-4 or recurrent Grade 1-2 pneumonitis

- Colitis – Grade 4
- Immune-mediated Hepatitis – Grade 4
- Immune-mediated Endocrinopathies – (excluding endocrinopathies controlled with hormone replacement therapy)
 - Hyperthyroidism – Grade 4
- Immune-mediated Nephritis – Grade 3-4
- Infusion-related reaction – Grade 3 or 4
- Inability to reduce corticosteroid dose to 10mg or less of prednisone or equivalent per day within 6 weeks
- Persistent Grade 2 or 3 adverse reactions (excluding endocrinopathies controlled with hormone replacement therapy) that do not recover to Grade 0-1 within 4 weeks after last dose of pembrolizumab
- Any Grade 3-4 treatment-related adverse reaction that recurs
- Please refer to the FDA approved pembrolizumab prescribing information for more information.
- For treatment or dose modification related questions, please contact [name] (MedCon may also be used to contact MDs at [contact]).

8.2 Umbralisib dose reduction steps: If a subject undergoes a dose reduction, it should not be subsequently increased, even if the toxicity resolves to Grade 0. However, if further evaluation of the toxicity reveals the event was not related to umbralisib, this should be recorded in the medical record and dose re-escalation to the previous dose may be considered at the discretion of the investigator.

Drug	Starting Dose	1 st Dose Reduction	2 nd Dose Reduction
Umbralisib	800mg daily	600mg daily	400mg daily

Supportive care should be considered for any subject who experiences Grade \geq 2 cytopenias, or Grade \geq 1 non-hematologic toxicities.

NCI-CTCAE Grade	Umbralisib Dose Delay or modification
Hematologic Adverse Event	
Neutropenia	
Grade \leq 2 neutropenia	Maintain current umbralisib dose. Consider supportive care as warranted.
Grade 3 neutropenia	Maintain current umbralisib dose for first occurrence, consider supportive care. If recurrence or persistent Grade 3 after re-challenge, resume umbralisib at next lower dose level at discretion of the principal investigator/sub-investigator.
Grade 4 neutropenia or occurrence of neutropenic fever/infection	Delay umbralisib until Grade \leq 3 and/or neutropenic fever or infection is resolved; thereafter, resume at current dose. Consider supportive care. If recurrence after re-challenge, resume umbralisib at next lower dose level at discretion of the principal investigator/sub-investigator.
Thrombocytopenia	
Grade \leq 3 thrombocytopenia	Maintain current umbralisib dose level and provide supportive care as clinically warranted.
Grade 4 thrombocytopenia	Delay umbralisib until Grade \leq 3; thereafter, resume at current dose. Consider supportive care intervention as warranted. If recurrence after re-challenge, resume umbralisib at next lower dose level at discretion of the principal investigator/sub-investigator.
Hepatitis	
Grade 2-3 AST/ALT or total bilirubin increase	Delay umbralisib until resolution to Grade \leq 1. If the subject has baseline liver involvement and grade 2 abnormalities at baseline, treatment may continue unless it worsens to grade 3. For grade 3 toxicity, reduce the umbralisib dose to the next lower dose level upon resolution to Grade \leq 1.
Grade 4 AST/ALT or total bilirubin increase	Permanently discontinue umbralisib.
Immune related pneumonitis*	
Grade 1-2	Stop all therapy (umbralisib and pembrolizumab) and hold until complete resolution. Restart umbralisib at one lower dose level. Restart pembrolizumab at current dose. If recurrence after re-challenge, discontinue all treatment therapy.
Grade \geq 3	Discontinue all therapy (umbralisib and pembrolizumab).

* For sinopulmonary infections clearly not related to immune-mediated pneumonitis, umbralisib may be continued at investigator's discretion. While pneumonitis has been minimal with umbralisib, it is a reported adverse event associated with other PI3K delta inhibitors. *Pneumocystis jiroveci* pneumonia (PCP) and anti-herpetic viral prophylaxis must be instituted as outlined in 7.2.1.

Diarrhea and/or colitis	
Diarrhea grade \leq 2	Maintain current umbralisib dose level if tolerable or hold and then resume at current dose level once has resolved. NOTE: If persistent grade 2 diarrhea, despite supportive care, delay umbralisib until \leq grade 1. If recurrence after rechallenge, resume umbralisib at current dose or next lower dose level at discretion of the principal investigator/sub-investigator.
Diarrhea \geq 3	Withhold umbralisib until Grade \leq 1. Resume umbralisib at current dose or next lower dose level as per discretion of principal investigator/sub-investigator. If recurrence after rechallenge, resume umbralisib at next lower dose level at discretion of the principal investigator/sub-investigator.
Colitis (all grades)	Hold umbralisib. Treat with supportive care and after resolution of colitis, resume umbralisib at next lower dose level
All other non-hematological events	
Grade \leq 2	Maintain current umbralisib dose level.
Grade \geq 3	Withhold umbralisib until Grade \leq 1. If recurrence after rechallenge, resume umbralisib at current dose or next lower dose level at the discretion of the principal investigator/sub-investigator.

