- An important medical event (i.e., AEs/ADRs that might not be immediately life-threatening, or result in death or hospitalization might be considered serious when, based upon appropriate medical and scientific judgment, they might jeopardize the patient/subject or might require medical or surgical intervention to prevent one of the other serious outcomes listed above);

- Any suspected transmission via a medicinal product of an infectious agent.

Grade

Grade is defined as the severity of the adverse event. The CTCAE Version 5.0 must be used to determine the grade of the adverse event. If toxicity is not listed in the CTCAE use the following general criteria for grading.

- 0 – No adverse event or within normal limits
- 1 – Mild adverse event
- 2 – Moderate adverse event
- 3 – Severe adverse event
- 4 – Life-threatening or disabling adverse event
- 5 – Fatal adverse event

Attribution

Attribution is defined as the determination of whether an adverse event is related to a medical treatment or procedure. The investigator or authorized sub-investigator will assess attribution according to the following categories:

- *Unrelated*: the adverse event is *clearly NOT related* to therapy
- *Unlikely*: the adverse event is *doubtfully related* to therapy
- *Possible*: the adverse event *may be related* to therapy
- *Probable*: the adverse event is *likely related* to therapy
- *Definite*: the adverse event is *clearly related* to therapy

Unexpected Adverse Event

An *unexpected adverse event* is any adverse event that is not listed in the current Investigator's Brochure, package insert, protocol, or associated documents; or the specificity or severity of which is not consistent with these documents.

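### A first Grade 4 pembrolizumab-related non-hematological reaction with no row of its own (e.g. myocarditis) has no permanent stop at onset in 8.1.1 or 8.1.2, and the default permits resumption after recovery

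*Combined protocol and SAP*

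**What the plan says.** The lead-in to 8.1.1 states a general hold: "Pembrolizumab must be withheld for drug-related toxicities and severe or life-threatening AEs as per the below criteria". It then gives the default after a hold: "may resume upon recovery to grade 0 or 1 toxicity unless otherwise noted below". The rows that follow name colitis, hyperthyroidism, hypophysitis, nephritis, pneumonitis and hepatitis. Everything else that is non-hematological falls to the last row: "Other treatment-related toxicity, severe or Grade 3; may require high-dose systemic corticosteroids (based on severity"). That row goes on: "Restart pembrolizumab if the adverse reaction remains at grade 0 or 1 and steroid dose is" at most 10 mg, after a taper of at least one month.

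The same lead-in recommends discontinuation when a drug-related toxicity has not come down to Grade 0-1 within 4 weeks of onset.

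Section 8.1.2 lists permanent stops. By toxicity and grade these are pneumonitis 3-4 (or recurrent 1-2), colitis 4, hepatitis 4, hyperthyroidism 4, nephritis 3-4 and infusion-related reaction 3-4. The general toxicity criteria are failure to get steroids down to 10 mg within 6 weeks, "Persistent Grade 2 or 3 adverse reactions" that do not recover within 4 weeks of the last dose, and "Any Grade 3-4 treatment-related adverse reaction that recurs". Both the catch-all row and the stop list close with a pointer to the prescribing information.

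**The concern.** Section 3.1.1 lists uveitis, myositis, myelitis and myocarditis among the clinically important pembrolizumab reactions in Hodgkin lymphoma, and none has a row in 8.1. If one of them occurs at Grade 4 for the first time and then resolves, the written rules leave re-exposure open. For colitis or hepatitis of the same grade they do not. The protocol gives no reason for the difference, and two investigators could handle the same event differently.

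Section 7.5 itself anticipates that the combination may raise the rate of immune-related events, and safety is a secondary objective. One of the two events behind the earlier suspension was a Grade 3 rash. Rash also has no row, so the catch-all has already been relevant in this trial.

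**Working it through.** **Step 1: what happens at a first Grade 4, by named toxicity.** The plan states no figure here, so the check is a row count over 8.1.1 and 8.1.2.

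| Named non-hematological toxicity | First Grade 4 |
|---|---|
| Pneumonitis | stop |
| Colitis | stop |
| Hepatitis | stop |
| Hyperthyroidism | stop (heading excludes endocrinopathies controlled by hormone replacement) |
| Nephritis | stop |
| Infusion-related reaction | stop |
| Hypophysitis | hold |

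Stops: 6 of 7. The exception is written out: "Hypophysitis- Grade 2-4; administer high-dose systemic corticosteroids". So where the protocol intends a hold at Grade 4, it can say so.

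**Step 2: does any general rule stop a first Grade 4 event with no row, at onset?**

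- Catch-all row: it names severe or Grade 3. In the general grading list of 12.2, Grade 3 is the severe grade and Grade 4 is "Life-threatening or disabling adverse event". If the row is still read to include Grade 4, it ends in a restart, not a stop.
- Recurrence rule: needs a second event.
- Persistence rule: names Grade 2 or 3 only.
- Steroid rule: acts at 6 weeks.
- 4-week rule in 8.1.1: covers any grade, but is a recommendation and acts at 4 weeks.

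Number that require a stop at onset: 0. What remains is the lead-in: hold, then resumption allowed at Grade 0-1.

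**Step 3: how often this could arise.** Section 3.1.1 gives any-grade rates on pembrolizumab of 1% for uveitis, 1% for myositis, 0.5% for myelitis and 0.5% for myocarditis. With at most one per subject, the sum is 1 + 1 + 0.5 + 0.5 = 3.0%. In 20 subjects, 20 × 0.03 = 0.60 events of any grade are expected, and the chance of at least one is 1 − 0.97^20 = 45.6%.

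The documents do not give the Grade 4 share, s. Assume s from 10% to 50%. The chance of at least one Grade 4 event is 1 − (1 − 0.03s)^n:

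| s | n = 20: expected | n = 20: chance | n = 15: expected | n = 15: chance |
|---|---|---|---|---|
| 10% | 0.06 | 1 − 0.997^20 = 5.8% | 0.045 | 1 − 0.997^15 = 4.4% |
| 50% | 0.30 | 1 − 0.985^20 = 26.1% | 0.225 | 1 − 0.985^15 = 20.3% |

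The second pair of columns uses the 15 subjects that section 7.5 says are still to be enrolled.

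**Step 4: from event to changed management.** Events that fail the 4-week or 6-week conditions are already directed to a stop. If, purely for illustration, half of the Grade 4 events met the restart conditions, the range in 20 subjects would be 1 − 0.9985^20 = 3.0% to 1 − 0.9925^20 = 14.0%, before allowing for investigators who would stop anyway.

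**The case against.** The strongest reply is that 8.1 is not meant to stand alone. Pembrolizumab is a commercial drug, section 3.1 refers to the current label, and the pointer to the prescribing information is repeated in both sections. The label may contain a Grade 4 rule. This stands in part: its content cannot be seen here, so nothing can be claimed about agreement or conflict with it. But the protocol offers it as further information, and the protocol's own text states a resume rule.

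A second reply is that re-exposure is already hard to reach. The 4-week recommendation has no grade limit, the 6-week steroid rule applies to any toxicity, section 7.4.2 ends therapy when the protocol harms the subject, and a contact is named for dose questions. This stands, and it narrows the point to events that recover and taper in time.

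A third is that the wording is open to dispute. The 12.2 list applies only where CTCAE has no entry, and if severe meant exactly Grade 3, the phrase in the row would be redundant. That is fair, but the conclusion does not depend on it, because the wider reading leads to a restart.

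A fourth is that hold-and-reassess may be deliberate, since Grade 4 hypophysitis and Grade 4 hematological toxicity are held. Those holds are written out, however; nothing comparable is stated for the unlisted reactions.

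**Conclusion.** The gap is real and narrow. For a first Grade 4 non-hematological reaction to pembrolizumab that has no row, 8.1.1 and 8.1.2 set no permanent stop at onset, although 6 of the 7 named toxicities have one.

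A reader might infer more than the documents support. They do not require re-exposure; they permit it. They do not leave such events without any stop, because the 4-week and 6-week rules act later. And 6% to 26% (4% to 20% in the remaining 15) is not the chance that a subject is re-exposed. It is the chance of any Grade 4 event among the four reactions, and so an upper bound on how often these four would be managed differently. It rests on single-agent rates, at most one event per subject, and an assumed Grade 4 share of 10% to 50%. It leaves out other unlisted toxicities and any increase due to the combination, which the documents do not quantify.

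This is a cheap safety improvement rather than a major defect: an uncommon event, but a serious one for the subject concerned.

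**What to change.** Add one criterion to 8.1.2: permanently discontinue pembrolizumab at the first occurrence of any other Grade 4 non-hematological adverse reaction whose attribution to pembrolizumab is possible, probable or definite. Exclude hypophysitis (see 8.1.1), endocrinopathies managed by hormone replacement, asymptomatic laboratory abnormalities, and events attributed only to umbralisib.

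In 8.1.1, change the grade in the catch-all row to: Grade 3, or a Grade 4 event excluded in 8.1.2. The excluded events then keep a defined hold and restart, except that hypophysitis stays under its own row.

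The limits matter. A rule for any treatment-related Grade 4 event would stop pembrolizumab for a Grade 4 diarrhea due only to umbralisib, while 8.2 allows umbralisib itself to resume. Without the hypophysitis exclusion, the new line could override that row's explicit hold.

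Cost: one new line and one edited row in a single amendment, with no added visits, data or staff. The drawback is that a rare subject stopped before 6 cycles and without a CR may also lose umbralisib under 7.4.3.
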